## 9.10. EXPLORATORY ANALYSIS

To address the exploratory objective of characterizing the conversion to JZP-258 from non-Xyrem antiepileptic treatments, analyses including subjects from Pre-randomization Groups 2, 3, and combined will be provided. Analyses will include, but are not limited to, summaries of antiepileptic use, titration and duration of antiepileptics, as well as JZP-258 titration during the Optimized Treatment and Titration Period.

## 10. ANALYSIS AT THE END OF STUDY

For the final safety analysis, after all subjects have completed or discontinued the study, all safety summaries (as specified in [section 9.9](#)) will be updated based on all available safety data from all periods. Disposition, treatment exposure, concomitant medication, as well as all the relative safety analysis will also be updated.

## 11. DATA NOT SUMMARIZED OR PRESENTED

The other variables and/or domains not summarized or presented are:

- Comments

These domains and/or variables will not be summarized or presented, but will be available in the clinical study database, SDTM and/or ADaM datasets.

## APPENDIX 1. PROGRAMMING CONVENTIONS FOR OUTPUTS

### OUTPUT CONVENTIONS

Outputs will be presented according to the following:

- **Paper size, orientation, and margins:** The size of paper will be Letter. The page orientation will be landscape; Margins should provide at least 1 inch (2.54 centimeters) of white space all around the page, regardless of the paper size.
- **Fonts:** The font type ‘Courier New’ will be used as a default for tables and listings, with a font size of 8. The font color will be black. No **bolding**, underlining, *italics* or subscripting will be permitted. Super-scripts will be avoided, unless absolutely necessary. Single spacing will be used for all text.
- **SDTM Terminology:** When possible, SDTM controlled terminology (e.g., race) will be used in the tables, listings and figures outputs.

### DATES & TIMES

Depending on data available, dates and times will take the form yyyy-mm-ddThh:mm:ss.

### SPELLING FORMAT

English US, with the exception of the MedDRA SOCs and PTs for which British English will be used.

### PRESENTATION OF TREATMENT GROUPS

For outputs by Pre-randomization Groups, group will be presented as follows and in that order:

Pre-randomization Group	For Tables, Figures, and Listings
Pre-randomization Group 1: Subjects on Xyrem Only	Xyrem
Pre-randomization Group 2: Subjects on Xyrem and an Additional Anticataplectic	Xyrem + Anticataplectic
Pre-randomization Group 3: Subjects on Non-Xyrem Anticataplectic	Non-Xyrem Anticataplectic
Pre-randomization Group 4: Subjects Not Treated with an Anticataplectic	Naive
Overall	Total

For outputs by treatment group, group will be presented as follows and in that order:

Treatment Group	For Tables, Figures, and Listings
JZP-258	JZP-258
Placebo	Placebo

## NUMBER OF DECIMAL PLACES TO BE PRESENTED

For descriptive statistics, the same number of decimal places as in the raw data will be presented when reporting minimum and maximum, 1 more decimal place than in the raw data will be presented when reporting mean and median, and 2 more decimal places than in the raw data will be presented when reporting SD. If the raw data has 3 decimals or more, 3 decimals will be presented for mean, SD, median, minimum, and maximum.

For percentages, 1 decimal place will be presented.

For LS means, LS mean differences, SEs, and CIs, 2 more decimal places than in the raw data will be presented. If the raw data has 3 decimals or more, 3 decimals will be presented.

For p-values, 4 decimal places will be presented.

## LISTINGS

All data collected on the electronic case report form (eCRF) will be presented in the data listings. The listings will be ordered by the following (unless otherwise indicated in the shells): randomized treatment group, Pre-randomization Group, subject number, date (where applicable), and time (where applicable).

For listings where non-randomized subjects are included, these will appear in a category after the randomized treatment groups labeled 'Not Randomized'.

## APPENDIX 2. PARTIAL DATE CONVENTIONS

### ALGORITHM FOR PRIOR, CONCOMITANT, AND POST MEDICATIONS

START DATE	STOP DATE	ACTION
Known	Known	
 
• If medication stop date < study drug first dose date, assign as prior;
 
• If medication start date ≤ study drug first dose date ≤ medication stop date ≤ study drug last dose date, assign as prior and concomitant;
 
• If (medication start date ≤ study drug first dose date) and (study drug last dose date ≤ medication stop date or medication is ongoing), assign as prior, concomitant, and post;
 
• If study drug first dose date ≤ medication start date ≤ medication stop date ≤ study drug last dose date, assign as concomitant;
 
• If (study drug first dose date ≤ medication start date ≤ study drug last dose date) and (study drug last dose date ≤ medication stop date or medication is ongoing), assign as concomitant, and post;
 
• If study drug last dose date < medication start date, assign as post
 

	Partial	Impute stop date as latest possible date (i.e. last day of month if day unknown or 31 st December if day and month are unknown), then: 
 
• If medication stop date < study drug first dose date, assign as prior;
 
• If medication start date ≤ study drug first dose date ≤ medication stop date ≤ study drug last dose date, assign as prior and concomitant;
 
• If (medication start date ≤ study drug first dose date) and (study drug last dose date ≤ medication stop date or medication is ongoing), assign as prior, concomitant, and post;
 
• If study drug first dose date ≤ medication start date ≤ medication stop date ≤ study drug last dose date, assign as concomitant;
 
• If (study drug first dose date ≤ medication start date ≤ study drug last dose date) and (study drug last dose date ≤ medication stop date or medication is ongoing), assign as concomitant, and post;
 
• If study drug last dose date < medication start date, assign as post
 

	Missing and medication is not ongoing	
 
• If medication start date < study drug first dose date, assign as prior, concomitant, and post;
 
• If study drug first dose date ≤ medication start date ≤ study drug last dose date, assign as concomitant and post
 
• If study drug last dose date < medication start date, assign as post
 

START DATE	STOP DATE	ACTION
Partial	Known	
Impute start date as earliest possible date (i.e. first day of month if day unknown or 1st January if day and month are unknown), then:
 
 
• If medication stop date < study drug first dose date, assign as prior;
 
• If medication start date ≤ study drug first dose date ≤ medication stop date ≤ study drug last dose date, assign as prior and concomitant;
 
• If (medication start date ≤ study drug first dose date) and (study drug last dose date ≤ medication stop date or medication is ongoing), assign as prior, concomitant, and post;
 
• If study drug first dose date ≤ medication start date ≤ medication stop date ≤ study drug last dose date, assign as concomitant;
 
• If (study drug first dose date ≤ medication start date ≤ study drug last dose date) and (study drug last dose date ≤ medication stop date or medication is ongoing), assign as concomitant, and post;
 
• If study drug last dose date < medication start date, assign as post
 

	Partial	
Impute start date as earliest possible date (i.e. first day of month if day unknown or 1st January if day and month are unknown) and impute stop date as latest possible date (i.e. last day of month if day unknown or 31st December if day and month are unknown), then:
 
 
• If medication stop date < study drug first dose date, assign as prior;
 
• If medication start date ≤ study drug first dose date ≤ medication stop date ≤ study drug last dose date, assign as prior and concomitant;
 
• If (medication start date ≤ study drug first dose date) and (study drug last dose date ≤ medication stop date or medication is ongoing), assign as prior, concomitant, and post;
 
• If study drug first dose date ≤ medication start date ≤ medication stop date ≤ study drug last dose date, assign as concomitant;
 
• If (study drug first dose date ≤ medication start date ≤ study drug last dose date) and (study drug last dose date ≤ medication stop date or medication is ongoing), assign as concomitant, and post;
 
• If study drug last dose date < medication start date, assign as post
 

	Missing and medication is not ongoing	
Impute start date as earliest possible date (i.e. first day of month if day unknown or 1st January if day and month are unknown), then:
 
 
• If medication start date < study drug first dose date, assign as prior, concomitant, and post;
 
• If study drug first dose date ≤ medication start date ≤ study drug last dose date, assign as concomitant and post
 
• If study drug last dose date < medication start date, assign as post
 

START DATE	STOP DATE	ACTION
Missing	Known	

• If medication stop date < study drug first dose date, assign as prior

• If study drug first dose date ≤ medication stop date ≤ study drug last dose date, assign as prior and concomitant

• If study drug last dose date < medication stop date or medication is ongoing, assign as prior, concomitant and post

	Partial	Impute stop date as latest possible date (i.e. last day of month if day unknown or 31 st December if day and month are unknown), then: 

• If medication stop date < study drug first dose date, assign as prior

• If study drug first dose date ≤ medication stop date ≤ study drug last dose date, assign as prior and concomitant

• If study drug last dose date < medication stop date or medication is ongoing, assign as prior, concomitant and post

	Missing	Assign as prior, concomitant, and post

**ALGORITHM FOR TREATMENT EMERGENCE OF ADVERSE EVENTS**

START DATE	STOP DATE	ACTION
Known	Known, Partial, Missing	
 
• If AE start date or worsened in severity < study drug first dose date, then not TEAE
 
• If study drug first dose date ≤ AE start date or worsened in severity ≤ (study drug last dose date + 30 days), then TEAE
 

Partial, but known components show that it cannot be on or after study drug first dose date	Known, Partial, Missing	Not TEAE
Partial, but known components show that it could be on or after study first dose date	Known	
 
• If AE stop date < study drug first dose date, then not TEAE
 
• If study drug first dose date ≤ AE worsened in severity or stop date ≤ (study drug last dose date + 30 days), then TEAE
 

or	Partial	If known components show that: 
 
• AE stop date < study drug first dose date, then not TEAE
 
• {[Study drug first dose date ≤ AE stop date ≤ (study drug last dose date + 30 days)] or [(study drug last dose date + 30 days) < AE stop date]}, then TEAE
 

Missing	Missing	Assumed TEAE

Note: Missing days will be assumed to be the first day of the month and missing months will be assumed to be the first month of the year for the purposes of determining if a partial date could be on or after the study first dose date (i.e. first day of month if day unknown or 1st January if day and month are unknown),.

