6.13.6 Adverse Events and Serious Adverse Event Recording and Reporting Timeframe

The Investigator must document all AEs and SAEs that occur during both the Main Study and the Open-Label Extension until the Final Study Visit or Early termination, regardless of their relationship to study drug or procedure. For those subjects who participate in the Main Study only and for Rollover Subject (progress directly into the Open-Label Extension), all AEs and SAEs will be documented from the time written informed consent is obtained at Visit 1. For Re-entry Subjects (complete the Main Study), all AEs and SAEs for the Open-Label Extension will be documented from the time written informed consent is obtained at Visit 18.

SAEs and immediately reportable experiences must be reported within 24 hours of first knowledge of the event by study personnel as described in Section 6.13.3 and Section 6.13.5.

If an Investigator becomes aware of an SAE within 30 days after the last dose of study drug, the event must be documented and reported as described in Section 6.13.3.

Any SAE assessed as related to study drug or procedure by the Investigator must be reported regardless of time after study termination.

Follow-up of Adverse Events and Serious Adverse Events 6.13.7

Adverse events assessed as not related to study drug or procedure, including clinically significant laboratory tests, ECGs, or physical examination findings, must be followed until the event resolves, the condition stabilizes, the event is otherwise explained, or the Final Study Visit occurs, whichever comes first.

AEs and SAEs assessed as related to study drug or procedure will be followed for as long as necessary to adequately evaluate the subject's safety, or until the event stabilizes, or the subject is lost to follow up. The outcome at the time of the Final Study Visit should be documented. If resolved, a resolution date should be provided, and for SAEs, a follow-up SAE Report form should be submitted indicating the resolution date.

The Investigator is responsible for ensuring that follow-up includes any supplemental investigations indicated to elucidate the nature and/or causality of the AE. This may include additional clinical laboratory testing or investigations, examinations, histopathological examinations, or consultation with other health care professionals as is practical.

> Confidential Page 64 of 148

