6.14 Removal of Subjects from the Trial or Study Drug

6.14.1 Reasons for Early Terminations

All subjects are free to withdraw from participation in this study at any time, for any reason, and without prejudice. The Investigator must withdraw any subject from the study if the subject states that he/she wants to stop participating in the study.

The Investigator, Jazz Pharmaceuticals or its designee may remove a subject from the study at any time and for any reason.

If any of the criteria below are met during the study, study drug administration must be stopped and the subject discontinued from the study.

- Suicide risk reported or assessed by C-SSRS
- 3-fold or greater elevation above the ULN of ALT or AST accompanied by an elevation of serum total bilirubin greater than two times the ULN
- Liver enzyme (AST, ALT) value greater than or equal to 5 times the ULN
- Creatinine > 176 μmol/L
- Positive alcohol screen
- Positive urine drug screen
- Positive pregnancy test

For all subjects who prematurely discontinue from the Main Study, an attempt should be made to perform all early termination assessments (same assessments as those performed at the final study visit). Subjects should be asked to return 2 weeks later for a safety follow-up visit.

The specific reason for the discontinuation should be documented on the termination eCRF. If a subject withdraws informed consent, the specific reason for withdrawing the informed consent should be stated.

Adverse events resulting in termination will be followed to the satisfactory resolution and determination of outcome as ascertained by the Investigator (and/or Jazz Pharmaceuticals or its designee). The data will be recorded on the appropriate eCRF.

Confidential Page 66 of 148

P-258 Jazz Pharmaceuticals

For all subjects who prematurely discontinue from the Open-Label Extension, an attempt should be made to perform all early termination assessments (same assessments as those performed at the final study visit). Subjects should be asked to return 2 weeks later for a safety follow-up visit.

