### 7.2. MISSING DATA

Missing or partially missing concomitant medications and AEs start and stop dates will be imputed as described in [APPENDIX 2](#). However, imputed dates will NOT be presented in the listings as their sole

purpose will be for the classification of the medications as past, concomitant or post (refer to [section 9.5](#)) and the classification of the AEs as prior, treatment-emergent or post (refer to [section 9.9.1](#)).

Missing cataplexy attacks data will be handled as described in [sections 9.8.1.3](#) and [9.8.1.5](#).

Missing questionnaire data will be handled as described in the following sections:

- ESS:
  - Individual item scores: [section 9.8.2.1](#)
  - Total score: [section 9.8.2.2](#)
- PGIC and CGIc: [section 9.8.3.2.1](#)
- CGIs: [section 9.8.4.1](#)
- SF-36:
  - Scales and overall components: [section 9.8.3.2.2](#)
- EQ-5D-5L:
  - Dimensions: [section 9.8.3.1.4](#)
  - Crosswalk index score: [section 9.8.3.3.3](#)
- PHQ-9: [section 9.9.5.2](#)

Missing safety data (other than PHQ-9) will not be imputed.

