### 9.9.1. ADVERSE EVENTS

AEs will be coded to SOC and PT using the MedDRA dictionary, version 19.1 and will be classified as follows:

- **Prior AEs** are defined as AEs that started on or after the signature of the Main Study informed consent but prior to the first dose of OL OTTP study drug;
- **For the overall summaries**, (TEAEs) are defined as any AEs that started or worsened in severity on or after the first dose of Open-Label study drug up to the last dose of study drug during the Open-Label Optimized Treatment and Titration period, Open-Label Stable-Dose Period, Double-Blind Randomized-Withdrawal Period or Open-Label Extension period (whichever is the latest) + 30 days.
- **For the DB RWP**, TEAEs are defined as any AEs that started or worsened in severity on or after the first dose of double-blind study drug up to 1) the last dose of double-blind study drug for subjects who did not enter the Open-Label Extension, 2) the first dose of study drug during the Open-Label Extension for subjects who rolled over into the Open-Label Extension immediately

after having completed the Main Study or 3) whichever occur first between the following two timepoints for subjects who rolled over into the Open-Label Extension after having re-entered into the study: last dose of double-blind study drug or first dose of study drug during the Open-Label Extension.

- **For the Main Study**, TEAEs are defined as any AEs that started or worsened in severity on or after the first dose of study drug up to the first day of the Open-Label Extension period for rollover subjects; or the first day of the Open-Label Extension period or the day of the last dose of study drug in the Double-Blind Randomized-Withdrawal period + 30 days (whichever is the earliest) for re-entry subjects.
- **For the OLE**, TEAEs are defined as any AEs that started or worsened in severity on or after the first dose of Open-Label study drug during the Open-Label Extension period up to the last dose of study drug + 30 days.
- **Post AEs** are defined as any AEs that started or worsened in severity after the last dose of study drug during the OTTP, SBP, RWP or OLE (whichever is the latest) + 30 days.

For OLE re-entry subjects, AEs occurring after their last dose of DB study drug, but prior to their first dose of OLE study drug will be considered as post AEs .

Only TEAEs will be summarized, but all AEs will be presented in the subject data listings.

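### SAP Appendix 2 has no treatment-emergence outcome for an AE with an incomplete start date and a known stop more than 30 days after last dose, so such an AE can be left out of the TEAE tables

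*SAP*

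**What the plan says.** SAP Section 7.2 sends incomplete AE dates to Appendix 2: "Missing or partially missing concomitant medications and AEs start and stop dates will be imputed as described in" that appendix. The treatment-emergence table there has one block for a start date that is missing, or partial but possibly on or after first dose. Within the block, the outcome depends on what is known about the stop date.

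- **Known stop, first rule:** "If AE stop date < study drug first dose date, then not TEAE".
- **Known stop, second and last rule:** the date must be on or after first dose, and "AE worsened in severity or stop date ≤ (study drug last dose date + 30 days), then TEAE".
- **Partial stop:** not TEAE if the stop is before first dose. TEAE if it lies between first dose and last dose + 30 days, and also in a further branch, "study drug last dose date + 30 days) < AE stop date]}, then TEAE".
- **Missing stop:** assumed TEAE.

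SAP Section 9.9.1 then states: "Only TEAEs will be summarized, but all AEs will be presented in the subject data listings".

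On how late a stop date can be, Protocol 6.13.7 ends follow-up of unrelated AEs at the Final Study Visit at the latest, whereas "AEs and SAEs assessed as related to study drug or procedure will be followed for as long as necessary". Protocol 6.14.1 adds: "Adverse events resulting in termination will be followed to the satisfactory resolution and determination of outcome".

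**The concern.** The known-stop row asks whether the AE ended inside the emergent window. SAP Section 9.9.1 and Protocol 9.11.1 define emergence by when the AE began or worsened. A late resolution date is no evidence against onset on treatment, yet here it takes the AE out of both rules. The outcome is also upside down: knowing the exact late stop date leaves the AE unclassified, while knowing only the month, or nothing, makes it a TEAE.

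What is at stake is the count in the TEAE tables: overall incidence, relationship to study drug, serious TEAEs, and TEAEs leading to discontinuation. Because follow-up past the Final Study Visit is reserved mainly for related and treatment-ending events, any loss would be selective rather than spread evenly over all AEs.

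**Working it through.** The plan gives no figure to reproduce, so the check runs stop dates through the rules as printed.

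**Inputs.** The rules are those of SAP Appendix 2. The dates are illustrative assumptions: first dose 10 January 2018 and last dose 1 May 2018, which is 112 days = 16 weeks × 7, the maximum Main Study treatment duration. Last dose + 30 days is 31 May 2018. The start date is missing, or partial but possibly on treatment.

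| Stop date | Position | Outcome as printed | With the late-stop branch added |
|---|---|---|---|
| Known, 9 January | first dose − 1 day | not TEAE | not TEAE |
| Known, 10 January | first dose | TEAE | TEAE |
| Known, 1 May | last dose | TEAE | TEAE |
| Known, 31 May | last dose + 30 | TEAE | TEAE |
| Known, 1 June | last dose + 31 | no rule | TEAE |
| Known, 15 June | last dose + 45 | no rule | TEAE |
| Known, 29 August | last dose + 120 | no rule | TEAE |
| Partial, June 2018 | wholly after last dose + 30 | TEAE | TEAE |
| Missing | unknown | TEAE by assumption | TEAE |

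Of the stop types tested, only a fully recorded late stop has no outcome.

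**Could another rule catch it?**

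1. *Worsening.* If worsening inside the window sits on the same record, the second rule gives TEAE despite a late stop. Protocol 6.13.2 has a change in severity entered as a new AE, so this will seldom rescue a record.
2. *Post AE.* SAP Section 9.9.1 defines this by start or worsening date, so it cannot place an AE with no start date.
3. *Default reading.* In the known-start row, a start after last dose + 30 days also meets no bullet, and Section 9.9.1 makes that a post AE. Elsewhere in the table, then, no match means not a TEAE. Code that leaves unmatched records unflagged would follow that pattern.
4. *Filling in the start.* The note under the table, which sets a missing day or month to the earliest possible, is only for judging whether a partial date could be on or after first dose. It does not change the stop-date test.

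**Can such stop dates occur?** The Safety Follow-up visit is at Week 18 in the Main Study (18 − 16 = 2 weeks after treatment) and Week 26 in the extension (26 − 24 = 2 weeks). With the schedule's 3-day allowance that is about 14 + 3 = 17 days, inside the 30. Unrelated AEs followed to that visit therefore do not normally reach the gap. Related AEs and SAEs, and AEs that ended participation, can.

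**Size of one record.** Against the planned enrolment of 185, one subject is 1/185 = 0.0054, or about 0.5 percentage points. This holds only if the subject has no other record under the same term, because SAP Section 9.9.1.1 counts a subject once per system organ class or preferred term.

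**The case against.** The strongest reply accepts the gap but doubts that it is often reached. It needs an incomplete start and a complete late stop on the same record. SAEs are reported within 24 hours of first knowledge, and contacts are mostly weekly during titration and over the first 10 extension weeks, so start dates should usually be known. Protocol 6.13.7 also asks for the outcome at the Final Study Visit, so an unresolved AE may stay in the database as ongoing with no stop date, and the missing-stop row then makes it a TEAE. In the overall definition, last dose is the latest in any period. For a subject who rolls over and completes the extension, a Main Study AE would have to outlast 24 weeks plus 30 days (168 + 30 = 198 days from the start of the extension). Finally, the table does not call the AE non-emergent. It is silent, and the adjacent row shows what was meant. If the known start month lies wholly on treatment, Section 9.9.1 alone would make it a TEAE.

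All of this stands as an argument about frequency. It does not close the gap: later resolution dates can be entered, Appendix 2 does not tell the programmer to fall back on Section 9.9.1, and a wholly missing start gives nothing to fall back on.

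**Conclusion.** Wrong as written, but minor. Coded to the text, an AE with an incomplete start and a known stop after last dose + 30 days is not flagged and leaves the TEAE summaries. The neighbouring rows show that this was not intended. The conclusion rests on the table as printed and on unmatched records being left unflagged. Few records are likely to be affected. The documents give no rate of incomplete AE dates, so no expected number can be stated.

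A reader might infer more than the documents support:

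- *That these events disappear.* They do not. All AEs are listed, and SAEs and AEs with an outcome of death have their own listings (SAP Sections 9.9.1.4 and 9.9.1.5).
- *That SAEs in general are exposed.* Protocol 6.13.7 takes SAEs past the Final Study Visit only when they are assessed as related. The termination rule in 6.14.1 adds AEs that ended participation.
- *That one record moves a double-blind arm by 1/65, or 1.5 percentage points.* SAP Section 9.9.1 gives that period its own window, ending at the last double-blind dose or the first extension dose, without the 30 days. The Appendix 2 cut-off is not that window, so the figure has no basis.
- *That every lost AE lowers incidence.* It does so only when it is the subject's sole record under that term.

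No efficacy conclusion is affected.

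**What to change.** In the known-stop row of the Appendix 2 treatment-emergence table, add the branch that the partial-stop row already has: a stop date later than study drug last dose date + 30 days is also TEAE. In the cases worked through above, this classifies every late known stop and changes no other outcome.

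Optionally, state in the known, partial and missing stop rows alike that an AE is not a TEAE when the known parts of its start date place onset after last dose + 30 days. This agrees with the Post AE definition in Section 9.9.1 and stops the wider rule from counting post-treatment events. It addresses a separate question and is not needed to close the gap.

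The cost is one line in the SAP and one programming condition, with a second of each if the option is taken. It is best settled before the data are unblinded, so that nobody has to decide case by case.

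### SAP Appendix 2 tests whether a partly dated AE could be treatment-emergent using its earliest possible date, which drops early TEAEs; SAP 9.9.1 also labels re-entry gap AEs both TEAE and post AE

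*SAP*

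**What the plan says.** **Partial AE dates (SAP Appendix 2, algorithm for treatment emergence).** The table sorts partial start dates by what the known parts of the date show. If they show that the start cannot be on or after first dose, the AE is not a TEAE, whatever its stop date. If the row "Partial, but known components show that it could be on or after study first dose date" applies, the stop date decides. An AE with both dates missing is assumed to be a TEAE. The Note below the table adds: "Missing days will be assumed to be the first day of the month and missing months will be assumed to be the first month", that is, January. It limits this imputation to one use: "for the purposes of determining if a partial date could be on or after the study first dose date".

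SAP 7.2 sends partial AE dates to this appendix and gives the purpose as "the classification of the AEs as prior, treatment-emergent or post". For partial medication starts, the appendix also says "Impute start date as earliest possible date".

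**Re-entry subjects (SAP 9.9.1).** Overall TEAEs run from the first open-label dose to the latest last dose, extension included, plus 30 days. Main Study TEAEs end at the first extension day or else at "the day of the last dose of study drug in the Double-Blind Randomized-Withdrawal period + 30 days (whichever is the earliest) for re-entry subjects". The section then says of re-entry subjects that "AEs occurring after their last dose of DB study drug, but prior to their first dose of OLE study drug will be considered as post", meaning post AEs. It also says "Only TEAEs will be summarized, but all AEs will be presented in the subject data listings".

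**The concern.** A partial date could fall on or after first dose if its *latest* possible value does. The Note tests the *earliest* value, so a start that may well be post-dose goes to the row for starts that cannot be.

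The table suggests this was not intended:

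- Under the Note, a partial start reaches the stop-date rows only if its imputed value is already on or after first dose. The branch for stop dates before first dose can then never apply to a partial start.
- An AE with no dates at all is kept as a TEAE, while one known to lie in the first-dose month is dropped.
- Earliest-date imputation does little harm in the medication table, because the stop date still decides whether a drug is concomitant. The AE exclusion row ignores the stop date.

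Safety is a secondary objective and only TEAEs are tabulated. The affected window is the start of open-label treatment. Protocol 1.3.4.1 and 1.3.4.3 report that Xyrem adverse reactions tended to come early and that most of those leading to discontinuation began in the first few weeks.

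The re-entry wording is a separate problem: two programmers could produce different Main Study and overall TEAE counts, each following a sentence of 9.9.1.

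**Working it through.** The plan gives no figure to reproduce, so the rules were applied literally.

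**1. The Note**

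Inputs: the earliest-date rule and the two partial-start rows (Appendix 2); Main Study treatment of 12 + 2 + 2 weeks = 112 days. Assumptions: first-dose dates spread evenly over a 365-day year, and first dose means the first open-label dose.

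- *Example.* With first dose on 15 May, a start of May becomes 1 May, which is before first dose, so the AE is not a TEAE. The true start could be any of 31 − 15 + 1 = 17 days on drug. Against a TEAE window of 112 + 30 = 142 days, 17/142 = 12%. A start of April is excluded and a start of June kept under either test; only the first-dose month differs.
- *How often.* The Note agrees with the row headings only when first dose falls on the 1st of a month: 12 of 365 dates. It misroutes the other 353 (96.7%). For year-only starts in the first-dose year it misroutes 364 of 365.
- *Width.* In a month of L days, the lost days summed over first-dose days 2 to L are L(L − 1)/2. Over the year: 7 × 465 + 4 × 435 + 378 = 5373, and 5373/365 = 14.7 days per subject; 14.7/112 = 13%. Across the 353 dates, the share of the month on or after first dose averages 50% (range 3% to 97%).
- *Double-blind period.* It starts about 98 days after first dose, so it begins in the first-dose month for 0 of 365 dates. Only a year-only start could reach it (266 of 365 dates).

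**2. The unmatched case**

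For a start that could be post-dose:

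| Stop date | Before first dose | First dose to last dose + 30 days | After last dose + 30 days |
|---|---|---|---|
| Known | Not TEAE | TEAE | no rule |
| Partial | Not TEAE | TEAE | TEAE |

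Unless a worsening is dated inside the window, the top-right cell is empty. Neither row can return a post AE, although SAP 7.2 names that as one of the three classes.

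**3. Re-entry gap**

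Example: first dose 1 March 2017, last double-blind dose 20 June 2017, extension 1 February to 18 July 2018.

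| Onset, days after last double-blind dose | Overall TEAE | Main Study TEAE | Re-entry post AE | General post AE |
|---|---|---|---|---|
| 10 | yes | yes | yes | no |
| 30 | yes | yes | yes | no |
| 31 | yes | no | yes | no |
| 206 | yes | no | yes | no |
| 225 | yes | no | yes | no |

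Every gap event carries two labels, and none meets the general post-AE definition, which starts only after the latest last dose + 30 days. None is a double-blind or extension TEAE.

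Such events are collected in two stretches: the safety follow-up, 14 to 17 days after double-blind treatment and so wholly within + 30 days; and from consent at Visit 18 to first extension dose, up to 30 days or 30 + 14 = 44 if extended. For the second stretch, Protocol 6.13.6 requires AE recording, while Protocol 9.11.1 treats events before the extension period as medical history.

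**The case against.** **A programmer would follow the row headings.** They sort on known components, and the unreachable branch points the same way, so this can be seen as an ambiguity to query. That is fair about intent. But the Note is the only operational instruction, and it says expressly that it governs this test. The SAP has to say which text prevails.

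**The numbers may be tiny.** This stands. 96.7% is only the share of dates that are not the 1st of a month. The count of partial dates is not given, and contacts are weekly during titration, when onset days should usually be known.

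**The unmatched case is rare.** This also stands. Under Protocol 6.13.6 and 6.13.7, AEs are documented to the final visit and unrelated ones are not followed beyond it. A known stop more than 30 days after last dose therefore arises mainly for related AEs still under follow-up.

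**Appendix 2 might be applied period by period.** If first dose meant the first double-blind dose, the double-blind tables would be exposed too. The appendix does not say. Its + 30-day limit matches the overall TEAE definition and not the double-blind one, which supports the open-label reading used here.

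**Few subjects are re-entry subjects.** They are those who finished double-blind treatment before approval of Amendment 4. This limits the size. It does not remove the conflict: treating the post-AE sentence as a specific override fails, because the Main Study + 30-day window is also written specifically for re-entry subjects.

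**Conclusion.** The concern holds. As written, the Note gives the wrong class for partial AE starts in the first-dose month (353 of 365 first-dose dates) and for nearly all year-only starts in the first-dose year. It affects on average 14.7 early open-label days per subject, always in the direction of fewer TEAEs. The known-stop row has a gap, and SAP 9.9.1 classifies re-entry gap events in two incompatible ways.

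The figures assume evenly spread first-dose dates and that first dose is the first open-label dose. The number of events lost cannot be derived from the documents and may be small. AEs with complete dates that occur on drug are classified correctly, every AE stays in the listings, the double-blind safety comparison is largely untouched, and no efficacy result changes. It should be corrected before the TEAE tables are programmed.

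**What to change.** 1. **Replace the Note.** A partial start cannot be on or after first dose only if its latest possible date (last day of the month, or 31 December) is before first dose; otherwise the rows decided by the stop date apply. Add an upper limit: if the earliest possible start is after last dose + 30 days, it is a post AE. State that first dose here means the first open-label dose, or say how partial dates are assigned to each period.
2. **Complete the known-stop row.** Class a possibly post-dose start with a stop after last dose + 30 days as a TEAE, subject to the same upper limit.
3. **State one rule in SAP 9.9.1 for re-entry gap events** and use it in the overall, Main Study and post-AE definitions. For example: TEAE up to the earlier of last double-blind dose + 30 days or first extension dose; later gap events are post AEs and lie outside the overall window. Delete or align the sentence that makes all gap events post AEs, and reconcile it with Protocol 6.13.6 and 9.11.1 for the time from Visit 18 to first extension dose. While editing, give the Main Study definition an end date for subjects who never enter the extension; it has none now.

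The cost is a few SAP sentences and a small program change. Some pre-dose events will be counted as TEAEs: with first dose on 15 May, those with unknown day that began on 1 to 14 May, unless their stop date shows they ended before first dose. That is the cautious direction, and the table's own row headings already choose it.
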